7.3. Blood Volume justification

Blood will be taken at each visit for safety laboratory assessments and immunologic assays (See table 3). Based on our calculation, the maximum blood volume taken within 28 days period is compliant with “*HREC guideline for maximum paediatric blood volumes for research purpose*”⁵. Additional blood sampling may occur at unscheduled visits, if needed, for safety laboratory tests.

8. SAFETY ASSESSMENTS

8.1. Adverse Events (AEs) and Concomitant Medications

8.1.1. Adverse Events (AEs)

AEs, either observed by the study physician (or his/her delegate) or reported by the participants (orally or in the participant diary), will be collected and assessed all along the study from the screening visit (VS) through the last long-term Follow-up/EOS visit (V8), in participants who have been enrolled.

AEs reported prior to first injection will be recorded in the participant's source data and in the eCRF and will be considered as non-treatment emergent AEs. Any new systemic effect that occurs between scheduled visits should be brought to the attention of the Investigator and recorded in the participant's source data and in the eCRF.

The severity of the general systemic symptoms will be graded according to the “Toxicity Grading Scale for Healthy Adult and Adolescent Volunteers Enrolled in Preventive Vaccine Clinical Trials” (Appendix 2).

8.1.2. Concomitant Medications

Use of concomitant medication will be recorded continuously starting from signing the ICF until the EOS visit (V8).

8.1.3. Vital signs

Vital signs (sitting or supine* BP, HR, RR, and body temperature) will be measured with the participant at rest at following visits:

- Screening visit (VS),
- 1st injection visit (V1)
 - For “Sentinel Groups”: before injection and 1 hour (± 15 min) after vaccine injection
 - For “Main Cohorts”: before injection and 1 hour (± 15 min) after vaccine/placebo injection
- Day 7 (V2) for “Sentinel Groups”
- 2nd injection visit (V4): before injection and 1 hour (± 15 min) after vaccine/placebo injection.
- Follow-up and long-term follow-up visits (V3; V5; V6; V7; V8)

* Vital signs can be measured in sitting or supine position as well as long as within 1 patient the measurements are always done in the same position.

During these visits, the investigator may order one re-test if they need to evaluate the evolution of one or several vital signs parameter(s) or to confirm the value observed. The reason and results of this re-test will be documented in the participant’s source data and in the eCRF.

Significant changes from baseline measurements performed at Screening visit, will be assessed, documented in the participant’s source data and recorded as AEs in the eCRF.

The severity of out of range vital signs will be graded according to the “Toxicity Grading Scale for Healthy Adult and Adolescent Volunteers Enrolled in Preventive Vaccine Clinical Trials” (Appendix 2).

8.1.4. Physical examination

A **complete** physical examination will be performed by a study physician at:

- Screening visit (VS) and long-term follow-up visits (V8)

A **directed** physical examination will be performed, in case of suspected symptoms, at:

- 1st injection visit (V1): before injection.
- Day 7 (V2) for “Sentinel Groups”
- Follow-up visit (V3)
- 2nd injection visit (V4): before injection.
- Follow-up visit (V6)

Significant changes from baseline examination performed at screening visit, will be assessed documented in the participant’s source data and recorded as AEs in the eCRF.

The severity of clinical abnormality will be graded according to the modified “Toxicity Grading Scale for Healthy Adult and Adolescent Volunteers Enrolled in Preventive Vaccine Clinical Trials” (Appendix 2).

8.1.5. Assessment of local Reaction of Injection Site

Assessment of local reaction will be made at the following time points:

- 1st injection visit (V1)
 - For “Sentinel Groups”: 1 hour (± 15 min) after vaccine injection

- For “Main Cohorts”: 1 hour (± 15 min) after vaccine/placebo injection.
 - Day 7 (V2) for “Sentinel Groups”
 - 2nd injection visit (V4): 1 hour (± 15 min) after vaccine/placebo injection.
 - Follow-up and long-term follow-up visits (V3; V5; V6)

Any local reaction will be assessed, documented in the participant’s source data and recorded in the eCRF.

The severity of local reaction will be graded according to the “Toxicity Grading Scale for Healthy Adult and Adolescent Volunteers Enrolled in Preventive Vaccine Clinical Trials” (Appendix 2).

8.1.6. 12-Lead ECG

A 12-lead ECG will be performed at Screening visit (VS)

During this visit, the investigator may order one re-test if they need to evaluate the evolution or to confirm the value observed during the first 12-lead ECG. The reason and results of this re-test will be documented in the participant’s source data and in the eCRF.

Any ECG abnormality determined by the study physician to be clinically significant will be assessed, documented in the participant’s source data and noted as an AE in the eCRF. Such abnormalities will be closely monitored until stabilized or resolved.

8.1.7. Safety Laboratory tests

Safety laboratory evaluations will be performed by laboratories of the study site at the following time points.

- Screening visit (VS)
- Day 7 (V2) for “Sentinel Groups”
- 2nd injection visit (V4): before injection
- Follow-up and long-term follow-up visits (V3; V6; V8)

The laboratory assessment variables are detailed in Appendix 1

During these visits, the investigator may order one re-test if they need to evaluate the evolution of one or several laboratory parameter(s) or to confirm the value observed. The reason and results of this re-test will be documented in the participant’s source data and in the eCRF.

Laboratory tests which are outside the normal range from the normal ranges defined by site laboratories will be assessed by the study physician. All abnormal laboratory test results that are considered to be clinically significant by the study physician will be documented in the participant’s source data and reported as an AE in the eCRF.

The severity of laboratories abnormalities will be graded according to the “Toxicity Grading Scale for Healthy Adult and Adolescent Volunteers Enrolled in Preventive Vaccine Clinical Trials” (Appendix 2).

8.1.8. Pregnancy Tests

Serum β -HCG will be tested in female subjects at Screening visit (VS). Urine pregnancy test will be performed at:

- 1st injection visit (V1) and at 2nd injection visit (V4) before injection
- Follow-up visit V6 (D56 \pm 3), V7 (D91 \pm 7) and V8 (D210 \pm 14)

During these visits, the investigator may order one re-test if they need to confirm the value observed. The reason and result of this re-test will be documented in the participant's source data and in the eCRF.

8.2. Participant Diary

The participant will receive a diary on each vaccination day (visit 1 and 4) for 14 \pm 1 days completion. They will be requested to record any local or systemic reaction (vaccination day included) and body temperature. In this frame, participants will receive a ruler to measure the size of local reaction if occurs and a thermometer to measure oral body temperature.

Solicited local and solicited systemic reactions will be assessed by the participants themselves by checking for presence of the listed symptoms and measuring the size of the affected area where appropriate (a template will be provided for local reaction grading, as shown in Appendix 3). The diary will also provide space for recording unsolicited AEs and concomitant medication.

Recording should be done approximately at the same time each day, starting on the day of vaccination.

The participants' diaries will be collected and verified for completeness by the investigator. Any symptoms recorded in the participant diaries will be documented in the source data by the investigator or authorized delegates. The investigator will re-evaluate the severity of the reported local and systemic reactions according to the "Toxicity Grading Scale for Healthy Adult and Adolescent Volunteers Enrolled in Preventive Vaccine Clinical Trials" (Appendix 2). After assessment of the Investigator, clinically significant symptoms (i.e. moderate/severe) and mild symptoms for which a treatment is required will be reported as Adverse Events in the eCRF.

The diary includes the following:

- **Solicited systemic AEs:** Myalgia (osteomuscular pain), rash, nausea, vomiting, fever (body temperature $\geq 38^\circ$), headache and fatigue.
- **Solicited local reaction to injection:** Pain, itching, erythema (redness), swelling, induration.

these should also be documented in the participant' source data and in the eCRF.

In addition, body temperature will be checked during 14 \pm 1 days following each injection and fever will be graded by the investigator according to "Toxicity Grading Scale for Healthy Adult and Adolescent Volunteers Enrolled in Preventive Vaccine Clinical Trials" (Appendix 2).

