2.2. Outcomes

2.2.1. Primary outcome measures

- Rate of solicited Adverse Event up to 14 days after each injection.
- Rate of unsolicited AE up to 28 days after each injection.
- Rate of serious adverse events (SAEs) serious adverse reactions (SARs), suspected unexpected serious adverse reactions (SUSARs) and adverse events of special interest (AESI) all along the study period.

Safety and tolerability will be assessed after each vaccination and participants will remain under observation at the study site for at least one hour for presence of any acute reactions and solicited events and by means of a diary completed by the participants for 14 days after each vaccination (from day 0 up to day 14 and from day 28 up to day 42). For each AE/SAE/AESI, the intensity and the relationship to vaccination will be reported and will be evaluated by the investigator.

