9.1.12. Reporting and follow-up of Adverse Events

9.1.12.1. Recording of AEs

All AEs, whether observed by the Investigator or designee or volunteered by or elicited from the subject, occurring after consent signature should be recorded individually in the CRF with the following information: the specific event or condition, the dates and times (using the 24 hour clock, where midnight is 00:00 and noon is 12:00) of occurrence, duration, severity, relationship to study medication, specific countermeasures, outcome, and whether considered non-serious or serious, drug-related or not. AEs will

be recorded from the time a subject has signed the ICF and throughout the study, including the follow up period. The solicited AEs should be reported by the investigator from the day of injection up to 14 days after each injection. The investigator should record all AEs for the whole period of the study.

An SAE must fulfill the requirements listed in the Section 9.1.3.

Outcome to Date of an AE are classified according to definitions described in section 9.1.9.

AEs will be coded by Data Management using the Medical Dictionary for Regulatory Activities (MedDRA) AE dictionary.

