12.3. Analysis of Safety objectives

All treated subjects will be included in the safety analysis. All adverse events will be coded according to coding dictionaries (MedDRA version 23.0 or higher) for System Organ Class (SOC) and Preferred Term (PT).

The adverse events will then be grouped by MedDRA preferred term into frequency tables according to SOC. These summaries will be presented by vaccination group and by interval of study observation. The overall frequencies per vaccine group as well as frequencies according to severity will be calculated for solicited (local and general) AEs, unsolicited AEs, serious AEs (SAEs), adverse events of special interest (AESI) and clinically significant abnormal laboratory values (grade 3 or 4). Solicited (local and systemic) and unsolicited AEs will be compared between treatment groups using Fisher-Freeman-Halton tests.

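### The protocol contradicts itself on whether mild, untreated solicited symptoms count as adverse events, and does not say which record feeds the primary solicited-AE rate

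*Protocol*

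**What the plan says.** The first primary outcome in Section 2.2.1 is "Rate of solicited Adverse Event up to 14 days after each injection". It carries no severity threshold. Section 12.3 plans overall frequencies per vaccine group and adds that "frequencies according to severity will be calculated for solicited (local and general) AEs".

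The recording rules differ from place to place:

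- **Section 8.2 (diary), filter.** Once the investigator has re-graded the local and systemic reactions, "clinically significant symptoms (i.e. moderate/severe) and mild symptoms for which a treatment is required will be reported as Adverse Events in the eCRF".
- **Section 8.2, later sentence.** After listing the solicited systemic AEs and local reactions, it adds: "these should also be documented in the participant' source data and in the eCRF". No grade or treatment condition is attached.
- **Section 8.1.1.** AEs "reported by the participants (orally or in the participant diary), will be collected and assessed all along the study".
- **Section 9.1.12.1.** The rule for CRF entry is: "All AEs, whether observed by the Investigator or designee or volunteered by or elicited from the subject, occurring after consent signature should be recorded individually". The same section adds: "The solicited AEs should be reported by the investigator from the day of injection up to 14 days after each injection".
- **Section 9.1.7.** A mild AE is one that needs little or no treatment and leaves daily activities undisturbed.
- **Section 8.1.5.** Any local reaction found at the scheduled assessments goes into the eCRF.

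**The concern.** The filter in Section 8.2 falls on the same local and systemic reactions that the first primary outcome counts. Read literally, an untreated mild headache or sore arm written in the diary is not reported as an Adverse Event. By Section 9.1.7 the same symptom is an AE, and by Section 9.1.12.1 it must be recorded individually.

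The trial is first-in-human and its primary objective is safety and tolerability. Two people who follow two different sections would count different events for the same primary outcome. If the count is taken from the filtered AE records, the any-grade rate is too low, and the grade 1 column required by Section 12.3 contains only the mild events that needed treatment.

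This is a matter for the protocol because it governs what sites enter during conduct. Section 2.2.1 requires intensity and relationship to vaccination to be reported for each AE. A later analysis plan cannot supply those assessments for symptoms that a site was told not to raise as AEs.

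**Working it through.** The protocol states no expected reactogenicity rate, and Section 12.6 says that no formal sample size calculation was made. There is therefore no figure to reproduce. The check is a comparison of the rules, followed by an illustration.

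**Step 1. One case under each rule.** Take a solicited symptom of grade 1, untreated, on a day inside the 14-day window.

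| Section | Is it an AE, or recorded? |
|---|---|
| 8.2, filter | Not reported as an AE |
| 8.2, later sentence | Documented in source and eCRF; AE status not stated |
| 8.1.1 | Collected and assessed if it is an AE; diary reports included |
| 8.1.5 | Entered in the eCRF if it is a local reaction seen at a visit; AE status not stated |
| 9.1.7 | An AE, of mild severity |
| 9.1.12.1 | Recorded individually; solicited AEs reported for 14 days |
| 2.2.1 and 12.3 | Counts if it is a solicited AE; no grade threshold; shown by severity |

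The first row cannot be reconciled with Sections 9.1.7 and 9.1.12.1. The second and fourth rows preserve data but do not say that these entries form the numerator of the rate.

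**Step 2. Consequence under each reading.**

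- If the solicited items documented in the eCRF feed the rate, nothing is lost.
- If the filtered AE records feed the rate, then

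  reported rate = true any-grade rate × (1 − s),

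  where s is the share of affected subjects whose symptoms are only mild and untreated.

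**Step 3. Illustration.** The group size of 24 vaccinees comes from Section 12.6. The true rate of 60% and the range of s from 50% to 80% are assumptions.

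| s | Reported rate | Expected vaccinees counted, of 24 |
|---|---|---|
| 0 (no filter) | 60% | 24 × 0.60 = 14.4 |
| 50% | 0.60 × 0.50 = 30% | 24 × 0.30 = 7.2 |
| 80% | 0.60 × 0.20 = 12% | 24 × 0.12 = 2.9 |

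**The case against.** The strongest reply is that Section 8.2 can be read as describing two records: all solicited items captured as such, with the clinically significant ones also raised as Adverse Events. The later sentence in that section supports this, as do the unfiltered 14-day rule in Section 9.1.12.1, the local-reaction rule in Section 8.1.5, and the fact that the diary list is itself headed as solicited AEs. A table by severity also makes more sense if grade 1 is complete. Diary symptoms are kept in source documents in any case, and the halting rules in Sections 4.8 and 4.9.1 do not turn on untreated grade 1 symptoms.

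Much of this stands. A reader might infer that the primary rate will certainly be understated. The documents do not support that, because the two-record reading is open and under it no event is lost. A reader might also infer that the greater part of grade 1 reactogenicity would disappear. No figure in the protocol gives the untreated share, so that cannot be said either. The choice of source dataset is often left to the analysis plan, and its absence here would not by itself be a finding.

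What the reply does not remove is the contradiction. The two-record reading has to be inferred. The word also in the later sentence sets documentation beside being reported as an AE, without making one equal to the other, while the primary outcome is worded as a rate of adverse events.

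**Conclusion.** The protocol is wrong as written. Section 8.2 denies AE status to symptoms that Section 9.1.7 defines as AEs and Section 9.1.12.1 requires to be recorded, and no section says which record supplies the first primary outcome.

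The harm is conditional. If the filtered AE records supply the numerator, untreated grade 1 events drop out, the any-grade rate is understated, and the grade 1 column shows treated events only. If the documented solicited items supply it, the rate is unaffected. The size in the first case cannot be derived from the documents. The fall from 60% to between 30% and 12% rests entirely on the assumed true rate and the assumed 50% to 80% share, and shows only how sensitive the rate is to the rule.

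**What to change.** Amend Section 8.2 so that the severity and treatment filter does not apply to solicited symptoms, and bring it into line with Sections 8.1.1, 9.1.7 and 9.1.12.1. State that every solicited symptom of grade 1 or higher in the 14-day window after each injection, treated or not, is entered in the eCRF with its grade and counted in the rate of solicited AEs.

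The cost is amendment wording and more eCRF rows. The diary already collects the information. The reported rates may be higher than they would be under the filter.

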8.3. Measles virus shedding assessment

Nasal swab, saliva, blood and urine sample will be collected in the 6 participants of the "Sentinel Groups" for performing a measles virus shedding assessment at the following time points:

- 1st injection visit (V1)
- Day 7 (V2)

- Follow-up visit (V3)
- 2nd injection visit (V4)
- Follow-up visit (V5)

Central laboratory will be used for analysis of all specimens collected.

The procedures of sample collection, preparation, storage, shipping and analysis will be described in detail in a study specific Lab-Manual.

8.4. Immunological sample handling

Blood samples will be drawn for immunological assessments at the following time points:

- 1st injection visit (V1): before injection
- 2nd injection visit (V4): before injection.
- Follow-up and long-term follow-up visits (V3; V5; V6; V7)

Central laboratories will be used for analysis of all specimens collected.

The procedures of sample collection, preparation, storage, shipping and analysis will be described in detail in a study specific Lab-Manual.

8.5. Measles virus shedding analysis

The shedding of infectious measles virus particles will be determined from the “sentinel Groups”, i.e. six immunized participants treated in an unblinded and non-randomized manner in cohort A and B. The samples will be analyzed by quantitative real-time Polymerase Chain Reaction (qPCR) to detect measles virus RNA. Any PCR positive sample will be further tested in an in vitro infectivity assay for the presence of infectious virus. The Measles virus shedding analysis will be performed at Texcell, Evry, France.

8.6. Calendar of study

- Provisional start recruitment date: Q2 2020
- Provision start enrollment date : Q3 2020
- Provisional inclusion duration: approximately 6 weeks
- Patient’s participation duration: approximately 7 months
- Projected study duration: approximately 15 months
- Data archiving duration: 25 years after the completion of the study
- Biobanks duration: 15 years

9. SAFETY AND PHARMACOVIGILANCE

9.1. DEFINITION

9.1.1. Adverse Event (AE)

An Adverse Event is defined as unfavorable and unintended sign (including an abnormal laboratory finding, for example), symptom, or disease temporally associated with the use of a medicinal product, whether or not considered related to the investigational medicinal product.

AEs do not include the following:

- Stable or intermittent chronic conditions (such as myopia requiring eyeglasses) that are present prior to study entry and do not worsen during the study
- Medical or surgical procedures (e.g., surgery, endoscopy, tooth extraction, transfusion). The condition that leads to the procedure is an AE if not present at baseline
- Hospitalization for elective surgery planned prior to study (situation where an untoward medical occurrence has not occurred)

AE will be graded according to the “Toxicity Grading Scale for Healthy Adult and Adolescent Volunteers Enrolled in Preventive Vaccine Clinical Trials” (Appendix 2).

9.1.2. Adverse Reaction (AR)

An adverse reaction (AR) is any untoward or unintended response in a participant to an IMP. This means that a causal relationship between the IMP and an AE is at least a reasonable possibility, i.e., the relationship cannot be ruled out. All cases judged by the reporting Investigator as having a reasonable suspected causal relationship to an IMP (i.e. possibly, probably or definitely related to an IMP) will qualify as AR.

9.1.3. Serious Adverse Events (SAEs)

An SAE is any AE occurring at any dose that suggest a significant hazard or side effect, regardless of the Investigator or Sponsor’s opinion on the relationship to the investigational product and that results in, but may not be limited to, any of the following outcomes:

- death (regardless of the cause)
- a life-threatening adverse event or suspected adverse reaction
- a persistent or significant disability/incapacity or a substantial disruption of the ability to conduct normal life functions
- An inpatient hospitalization or prolongation of existing hospitalization
- An important medical event (that may not result in death, be life-threatening, or require hospitalization) that may be serious when, based upon appropriate medical judgment, they may jeopardize the subject and may require medical or surgical intervention to prevent one of the outcomes listed above.
- a congenital anomaly or birth defect

9.1.4. Serious adverse drug reaction (SADR)

An event (expected or unexpected) that is both serious and, in the opinion of the reporting investigator or Sponsors, believed to be possibly, probably or definitely due to an IMP, based on the information provided.

